9.3.2.3 PD Population Analysis (Weeks 2, 4, 8 and 12)

9.3.2.3.1 FGF19

A descriptive summary will be provided for FGF19 concentrations, change from Baseline and the percentage change from baseline using 8-number summary by visit and treatment group.

Change from Baseline and the percentage change from baseline in the FGF19 for each time point by visit, with the week 12 visit being considered the primary visit of interest, will be analyzed using an ANCOVA model with treatment as fixed effect and the associated baseline value as covariate. Least squares means and standard errors will be presented for each visit, p-value and 2-sided 95% confidence interval for treatment differences will be presented for each visit. Significance tests will be based on least-squares means using a two-sided $\alpha = 0.05$.

Mean \pm SD and change from baseline for FGF19 values by visit and treatment group will be plotted.

A by-subject listing will be provided for observed and derived variables.

9.3.2.3.2 C4

A descriptive summary will be provided for C4 concentrations, change from Baseline and the percentage change from baseline using 8-number summary by visit and treatment group.

Change from Baseline and the percentage change from baseline in the C4 for each time point by visit, with the week 12 visit being considered the primary visit of interest, will be analyzed using an ANCOVA model with treatment as fixed effect and the associated baseline value as covariate. Least squares means and standard errors will be presented for each visit, p-value and 2-sided 95% confidence interval for treatment differences will be presented for each visit. Significance tests will be based on least-squares means using a two-sided $\alpha = 0.05$.

Mean \pm SD and change from baseline for C4 values by visit and treatment group will be plotted.

A by-subject listing will be provided for observed and derived variables.

9.3.2.3.3 Bile Acid

A descriptive summary will be provided for bile acid concentrations, change from Baseline and the percentage change from baseline using 8-number summary by visit and treatment group.

Change from Baseline and the percentage change from baseline in the bile acid for each time point by visit, with the week 12 visit being considered the primary visit of interest, will be analyzed using an ANCOVA model with treatment as fixed effect and the associated baseline value as covariate. Least squares means

and standard errors will be presented for each visit, p-value and 2-sided 95% confidence interval for treatment differences will be presented for each visit. Significance tests will be based on least-squares means using a two-sided $\alpha = 0.05$.

Mean \pm SD and change from baseline for Bile Acid values by visit and treatment group will be plotted.

A by-subject listing will be provided for observed and derived variables.

9.3.3 PK/PD Analysis at Week 12 (Correlations)

Scatterplots (including correlations) will be generated comparing the PD parameters or concentration to the PK parameter or concentration data or relevant lab data by treatment group.

9.3.3.1 PK/PD Subgroup Analysis

This will be done for all subjects in the PK/PD substudy. The following scatterplots with one regression line and additional plots will be generated:

- AUC₀₋₈ in FGF19 with PK parameter AUC_{last} (Day 1 and Day 84)
- AUC₂₋₈ in FGF19 with PK parameter AUC_{last} (Day 1 and Day 84)
- AUC₀₋₈ in C4 with PK parameter AUC_{last} (Day 1 and Day 84)
- AUC₂₋₈ in C4 with PK parameter AUC_{last} (Day 1 and Day 84)
- Percentage change from Baseline in AUC₀₋₈ FGF19 with PK parameter, AUC_{last} (Week 12)
- Percentage change from Baseline in AUC₂₋₈ FGF19 with PK parameter AUC_{last} (Week 12)
- Percentage change from Baseline in AUC₀₋₈ C4 with PK parameter AUC_{last} (Week 12)
- Percentage change from Baseline in AUC₂₋₈ C4 with PK parameter AUC_{last} (Week 12)
- Percentage change from Baseline in Bile Acid (predose Week 12) with PK parameter AUC_{last} (Week 12)
- Percentage change from Baseline in ALT (predose Week 12) with percentage change from Baseline in AUC₀₋₈ FGF19 (Week 12)
- Percentage change from Baseline in ALT (predose Week 12) with percentage change from Baseline in AUC₂₋₈ FGF19 (Week 12)
- Percentage change from Baseline in ALT (predose Week 12) with percentage change from Baseline in AUC₀₋₈ C4 (Week 12)
- Percentage change from Baseline in ALT (predose Week 12) with percentage change from Baseline in AUC₂₋₈ C4 (Week 12)
- Percentage change from Baseline in ALT (predose Week 12) with percentage change from Baseline in PK parameter AUC_{last} (Week 12)

- Percentage change from Baseline in FGF19 (predose Week 12) with PK parameter C_{max} (Week 12)
- Percentage change from Baseline in C4 (predose Week 12) with PK parameter C_{max} (Week 12)
- Percentage change from Baseline in Bile Acid (predose Week 12) with PK parameter C_{max} (Week 12)
- Box Plot Comparison of EDP-305 AUC_{last} and C_{max} at Day 1 and Week 12 by Pruritus Status
- Box Plot Comparison of Percent Change from Baseline in C4 AUC_{0-8} by Pruritus Status
- Box Plot Comparison of Percent Change from Baseline in C4 AUC_{2-8} by Pruritus Status

9.3.3.2 PK/PD Population Analysis

This will be done for all subjects (PK/PD substudy and population PK/PD). The following scatterplots with one regression line will be generated:

- Percentage change from Baseline in ALT (Predose Week 12) with the percentage change from Baseline in FGF19 (Predose Week 12)
- Percentage change from Baseline in ALT (Predose Week 12) with the percentage change from Baseline in C4 (Predose Week 12)
- Percentage change from Baseline in ALT (Predose Week 12) with the percentage change from Baseline in Bile Acid (Predose Week 12)
- Percentage change from Baseline in ALT (Predose Week 12) with EDP-305 concentration value (predose at Week 12)
- Percentage change from Baseline in AST (Predose Week 12) with the percentage change from Baseline in FGF19 (Predose Week 12)
- Percentage change from Baseline in AST (Predose Week 12) with the percentage change from Baseline in C4 (Predose Week 12)
- Percentage change from Baseline in AST (Predose Week 12) with the percentage change from Baseline in Bile Acid (Predose Week 12)
- Percentage change from Baseline in AST (Predose Week 12) with the EDP-305 concentration value (Predose Week 12)
- Percentage change from Baseline in GGT (Predose Week 12) with the percentage change from Baseline in FGF19 (Predose Week 12)
- Percentage change from Baseline in GGT (Predose Week 12) with the percentage change from Baseline in C4 (Predose Week 12)

-
- Percentage change from Baseline in GGT (Predose Week 12) with the percentage change from Baseline in Bile Acid (Predose Week 12)
 - Percentage change from Baseline in GGT (Predose Week 12) with EDP-305 concentration value (Predose Week 12)
 - Percentage change from Baseline in Total Bilirubin (Predose Week 12) with the percentage change from Baseline in FGF19 (Predose Week 12)
 - Percentage change from Baseline in Total Bilirubin (Predose Week 12) with the percentage change from Baseline in C4 (Predose Week 12)
 - Percentage change from Baseline in Total Bilirubin (Predose Week 12) with the percentage change from Baseline in Bile Acid (Predose Week 12)
 - Percentage change from Baseline in Total Bilirubin with (Predose Week 12) EDP-305 concentration value (Predose Week 12)
 - Percentage change from Baseline in Alkaline Phosphatase (Predose Week 12) with the percentage change from Baseline in FGF19 (Predose Week 12)
 - Percentage change from Baseline in Alkaline Phosphatase (Predose Week 12) with the percentage change from Baseline in C4 (Predose Week 12)
 - Percentage change from Baseline in Alkaline Phosphatase (Predose Week 12) with the percentage change from Baseline in Bile Acid (Predose Week 12)
 - Percentage change from Baseline in Alkaline Phosphatase (Predose Week 12) with EDP-305 concentration value (Predose Week 12)
 - Percentage change from Baseline in FGF19 (Predose Week 12) with the percentage change from Baseline in C4 (Predose Week 12)
 - Percentage change from Baseline in FGF19 (Predose Week 12) with the percentage change from Baseline in Bile Acid (Predose Week 12)
 - Percentage change from Baseline in FGF19 (Predose Week 12) with EDP-305 concentration value (Predose Week 12)
 - Percentage change from Baseline in C4 (Predose Week 12) with the percentage change from Baseline in Bile Acid (Predose Week 12)
 - Percentage change from Baseline in C4 (Predose Week 12) with EDP-305 concentration value (Predose Week 12)
 - Percentage change from Baseline in Bile Acid (Predose Week 12) with EDP-305 concentration value (Predose Week 12)

- Percentage change from Baseline in Cholesterol (Predose Week 12) with EDP-305 concentration value (Predose Week 12)
- Percentage change from Baseline in HDL (Predose Week 12) with EDP-305 concentration value (Predose Week 12)
- Percentage change from Baseline in LDL (Predose Week 12) with EDP-305 concentration value (Predose Week 12)
- Percentage change from Baseline in triglycerides (Predose Week 12) with EDP-305 concentration value (Predose Week 12)
- Correlation between Week 12 Predose EDP-305 concentrations and Adverse events occurring in at least 5% of the combined active subjects.

- Summary of Week 12 Predose EDP-305 concentrations for subjects with Grade 3 of Higher Adverse Events or Serious Adverse Events

- Summary of Week 12 Predose (or last predose) EDP-305 concentrations for subjects with week 12 completion by pruritus status
- Summary of Week 12 Predose (or last predose) EP-022679 concentrations subjects with week 12 completion by pruritus status
- Summary of Week 12 Predose (or last predose) EDP-305 concentrations for all subjects by pruritus status
- Summary of Week 12 Predose (or last predose) EP-022679 concentrations for all subjects by pruritus status

[REDACTED]

[REDACTED]

[REDACTED]

- [REDACTED]
- [REDACTED]
- [REDACTED]
- [REDACTED]
- [REDACTED]
- [REDACTED]

[REDACTED]

[REDACTED]

10 Safety Analyses

All safety analyses will be performed using all subjects in the safety population.

10.1 Treatment Emergent Adverse Events

Adverse events will be coded using MedDRA 20.1 (September 01, 2017) and graded by CTCAE version 5 (November 27, 2017). All safety analyses and listings will be reported using the safety population. An AE will be considered a Treatment-emergent AE (TEAE) if it first occurs or begins previous to and worsens on or after the first dose date and before the last dose date + 30 days. All TEAEs will be classified as being during the on-treatment period or during the follow-up period as follows:

- Events that occurred between first dose and 7 days after last dose are classified as on-treatment;
- Events occurring between 8-30 days after last dose are classified as follow-up.

Adverse Events will be summarized for the safety population by both on-treatment period and follow-up period separately by dose group.

The following events will not be identified as AEs in this study:

- Medical or surgical procedures (e.g., surgery, endoscopy, tooth extraction, etc.). The condition (the “triggering event”) that leads to the procedure are adverse events and will be reported as such.
- Pre-existing conditions present or detected prior to the first dose of study drug that do not worsen during the study.

Summaries of Adverse Events will include the following:

- AEs that occur during the screening period will be listed in the Medical History for each subject.
- An overall summary of all TEAEs. The number of events and the number and percentage of subjects reporting at least one TEAE will be reported
- The number and percentage of subjects reporting each TEAE, categorized by MedDRA system organ class and preferred term. Note that frequencies will be by subject not event.
- The number and percentage of subjects reporting each TEAE, categorized by MedDRA system organ class, preferred term and maximum CTCAE grade
- TEAEs experienced by $\geq 5\%$ of Subjects will be summarized by preferred term
- TEAE experienced by $\geq 5\%$ of Subjects categorized by MedDRA system organ class, preferred term and maximum CTCAE grade
- Treatment Related Adverse Events categorized by MedDRA system organ class and preferred term
- The number and percentage of TEAEs with outcome of death
- Serious TEAEs categorized by MedDRA system organ class and preferred term
- Serious TEAEs categorized by relationship to study drug, subjects with multiple events within each SOC or preferred term will be counted under the category of their most drug-related event within that SOC or preferred term
- TEAEs leading to study drug discontinuation categorized by MedDRA system organ class and preferred term

- Treatment Related TEAEs leading to study drug discontinuation categorized by MedDRA system organ class and preferred term
- Treatment Related TEAEs experienced by $\geq 5\%$ of Subjects will be summarized by preferred term
- Treatment Related TEAE experienced by $\geq 5\%$ of Subjects categorized by MedDRA system organ class, preferred term and maximum CTCAE grade

All adverse events (including non-treatment-emergent events) recorded on the eCRF will be listed for the Safety population

A summary of the number of subject deaths will be presented by treatment group. All death data will be listed.

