### 9.2.1 Documenting and Reporting Adverse Events

All AEs reported from the time of informed consent to the end-of-study for each subject will be recorded in the subject's source documents. For subjects who do not receive study drug (ie, screen failures), AEs will only be recorded in the source documents. For subjects enrolled into the study (ie, randomized), record all AEs in the subject's AE eCRF and Clinical Trials SAE Form (if applicable). The AE CRF will indicate if the event occurred prior to the first dose of study drug, during treatment, or during the post-dosing follow-up period. Record all AEs regardless of the intensity, seriousness, or relationship to study drug.

Grade AEs (serious and non-serious) in accordance with the NCI/CTCAE scale (available at [https://evs.nci.nih.gov/ftp1/CTCAE/CTCAE\\_4.03\\_2010-06-14\\_QuickReference\\_8.5x11.pdf](https://evs.nci.nih.gov/ftp1/CTCAE/CTCAE_4.03_2010-06-14_QuickReference_8.5x11.pdf)) as presented below:

- **Mild** (Grade 1) asymptomatic or mild symptoms; clinical or diagnostic observations only; intervention not indicated
- **Moderate** (Grade 2) minimal, local or noninvasive intervention indicated; limiting age-appropriate instrumental activities of daily living

- **Severe** (Grade 3) Severe or medically significant but not immediately life-threatening; hospitalization or prolongation of hospitalization indicated; disabling; limiting self care activities of daily living
- **Life-threatening** (Grade 4) Life-threatening consequences; urgent intervention indicated
- **Death** (Grade 5) Death related to the AE.

Any recurrence of an AE with similar causality to study drug will be reported as recurrence or exacerbation of the initial event, and not as a new event. Whenever possible, report AEs as a specific diagnosis or syndrome (eg, flu syndrome) rather than as individual signs or symptoms. If no specific diagnosis or syndrome is identified, AEs should be reported as separate and individual events.

An AE includes the following:

- Progression or exacerbation of the subject's underlying disease. Clinical sequelae that result from disease progression, such as pleural effusion or small bowel obstruction, are reportable as AEs.
- Pre-existing event that increases in frequency or intensity.
- Condition detected or diagnosed during the study period, even though it may have been present, in retrospect, prior to the first dose of study drug.

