Appendix 2 Adverse Event Start/Stop Date Imputation

Imputation Rules for Partial Dates (D = day, M = month, Y = year)

Parameter	Missing	Additional Conditions	Imputation
Start date for AEs	D	M and Y same as M and Y of first dose of study drug	Date of first dose of study drug
		M and/or Y not same as date of first dose of study drug	First day of month
	D and M	Y same as Y of first dose of study drug	Date of first dose of study drug
		Y prior to Y of first dose of study drug but same as Y of screening date	Date of screening date
	D, M, Y	None - date completely missing	Date of first dose of study drug
Stop date for AEs	D	M and Y same as M and Y of last dose of study drug	Date of last dose of study drug
		M and/or Y not same as date of last dose of study drug	Use last day of month
	D and M	Y same as Y of last dose of study drug	Date of last dose of study drug
		Y not same as Y of last dose of study drug	Use Dec 31
	D, M, Y	None - date completely missing	No imputation, but assume ongoing

Note: In all cases, if an estimated start date is after a complete stop date, use the first day of the stop date month.

Similarly, if the estimated stop date is before a complete or imputed start date, use the last day of the start day month.

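### TEAE dating ignores the CRF timing item, so some partly dated or Day 1 events that the site marked as pre-dose can be counted as on-treatment

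*SAP*

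**What the plan says.** **Collection.** Protocol 9.2.1 has all adverse events of randomized subjects recorded on the AE eCRF and adds: "The AE CRF will indicate if the event occurred prior to the first dose of study drug, during treatment, or during the post-dosing follow-up period". Protocol 9.1.1 defines a pretreatment event as one that arises after consent and before the first administration of study drug.

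**Definition.** Under SAP 10.1 an event is treatment-emergent "if it first occurs or begins previous to and worsens on or after the first dose date", with an upper limit 30 days after the last dose. TEAEs are then split into two periods: "Events that occurred between first dose and 7 days after last dose are classified as on-treatment", and "Events occurring between 8-30 days after last dose are classified as follow-up". The same section sends screening-period events to Medical History and says that pre-existing conditions which do not worsen are not adverse events.

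**Imputation of AE start dates (SAP Appendix 2).**
- Day missing, "M and Y same as M and Y of first dose of study drug": first dose date.
- Day missing, "M and/or Y not same as date of first dose of study drug": first day of that month.
- Day and month missing, "Y same as Y of first dose of study drug": first dose date.
- Day and month missing, earlier year that matches screening: screening date.
- Wholly missing: first dose date.

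A closing note moves an imputed start that falls after a complete stop date to the first day of the stop month. No row or note refers to the CRF timing item.

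**The concern.** Setting an uncertain onset to the first dose is a sensible cautious default when nothing is known about timing. Here the protocol says the site states the timing for every event, and the SAP applies the default without consulting that statement. The rule can then contradict the record. It also collides with SAP 10.1's own treatment of screening events and non-worsening pre-existing conditions, and no order of precedence is given, so two programmers could produce different tables.

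The frequency of adverse events is a secondary endpoint (Protocol 2.2.2), and SAP 10.1 reports on-treatment and follow-up events separately. At stake is the accuracy of the on-treatment TEAE tables, above all in the small placebo arm.

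**Working it through.** The plan states no figure on this point, so there is none to reproduce. The check applies the Appendix 2 rows and the 10.1 windows to events whose true period is known.

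**Three pre-dose records**
- First dose 20 June; headache dated June, ongoing, marked pre-dose. Month and year match the first dose, so the start becomes 20 June: on-treatment TEAE.
- The same event with a complete stop date of 15 June. The imputed 20 June falls after the stop, so the start becomes 1 June: not treatment-emergent. A partial stop date gives no such protection, because the note requires a complete one.
- An event with a complete Day 1 date that began before the dose. Protocol 7.1.3 places predose assessments on Day 1, and the Schedule of Assessments collects adverse events that day. It is pretreatment under Protocol 9.1.1 (before administration) but on or after the first dose date under SAP 10.1: on-treatment TEAE.

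**Share reclassified among pre-dose events with a partial or missing start and no complete pre-dose stop date**

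Assumptions: 365 consecutive first-dose dates, screening at Day -28, onset uniform over Days -28 to -1. That gives 365 × 28 = 10,220 combinations.

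- *Day missing.* For a first dose on day d of the month, min(d − 1, 28) of the 28 onset days fall in the same month. Summed over d, this is 462 for a 31-day month, 434 for a 30-day month and 378 for a 28-day month. Total: 7 × 462 + 4 × 434 + 378 = 5,348. Share: 5,348 / 10,220 = **52.3%**.
- *Day and month missing.* Onset falls in the previous year only for first doses on 1 to 28 January: 28 + 27 + … + 1 = 406 combinations. Share in the same year: 1 − 406 / 10,220 = **96.0%**. The rest take the screening date and stay pre-dose.
- *Wholly missing.* Every start becomes the first dose date: **100%**.
- *Any of the three with a complete stop date before the first dose:* **0%**.

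**Events that truly began 8 to 29 days after the last dose** (84 days of dosing, same first-dose dates, mean onset 18.5 days after the last dose)
- *Day missing:* the first-of-month row puts the start inside the on-treatment window in 1 − 12 × (18.5 − 7) / 365 = 62%.
- *Day and month missing:* onset lies on average 83 + 18.5 = 101.5 days after the first dose, so 101.5 / 365 = 28% fall in the next calendar year, for which Appendix 2 has no start row. The other 72% go to the first dose date.
- *Wholly missing:* 100% go to the first dose date.

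These follow-up shares take the true day as known. The CRF item alone does not establish it (see the objection).

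**Weight of one subject.** 119 subjects at 3:3:1 give 119 × 3/7 = 51 per active arm and 119/7 = 17 on placebo. One misclassified subject is 1/17 = 5.9 points on placebo and 1/51 = 2.0 points on an active arm. SAP 10.1 has several tables with a 5% threshold. If it is applied per arm, which the SAP does not say, one placebo subject crosses it.

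**The case against.** The best defence is that SAP 10.1 already excludes non-worsening pre-existing conditions and routes screening events to Medical History, so a known pre-dose event is not a TEAE. On that reading only precedence is unclear. This has force, but Appendix 2 is the operative dating rule and neither exclusion is tied to the CRF item or placed above the imputed date.

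The limits on consequence stand in full. The rule is cautious, is applied alike to every arm of a double-blind trial, and feeds descriptive tables without testing. All events, treatment-emergent or not, are listed. Adverse events are asked about at each visit of a study lasting about 20 weeks, so year-only or wholly missing dates should be rare. The CRF itself is not among the documents. If the timing item is derived from dates and not entered independently, it adds nothing when a date is partial.

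A reader might infer more than the documents support:
- *That emergence rests on dates alone.* It also rests on worsening.
- *That every partial date goes to the first dose.* Two Appendix 2 rows use the first of the month or the screening date.
- *That 52% and 96% apply to all pre-dose events with partial dates.* They apply only where no complete pre-dose stop date exists.
- *That any event marked as post-dosing follow-up is wrongly called on-treatment.* The CRF period starts after the last dose, whereas the SAP on-treatment window runs 7 days further, so an event on days 1 to 7 is rightly on-treatment under the SAP.

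**Conclusion.** The point holds as a minor defect in a stated rule. An event the site marked as pre-dose can be tabulated as an on-treatment TEAE if its start falls in one of the three imputation cases and no complete pre-dose stop date exists, or if it is dated Day 1 but preceded the dose. This conflicts with SAP 10.1's exclusion of non-worsening pre-existing conditions and with Protocol 9.1.1.

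The 52%, 96% and 100% rest on uniform onset over a 28-day screening period and describe only unprotected, partly dated or undated events. The documents do not give the number of such events, and it is probably small. The primary endpoint is unaffected, and nothing here shows a bias between arms.

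**What to change.** Amend SAP 10.1 and Appendix 2 to say that, when an AE start date is partial, missing or equal to the first dose date, the CRF timing item bounds the start:

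- **Marked pre-dose:** not treatment-emergent unless the event worsens. An imputed start is no later than the day before the first dose. State that this and the 10.1 exclusions take precedence over first-dose imputation.
- **Marked post-dosing follow-up:** the imputed start is after the last dose and consistent with any known month or year. Imputing to the day after the last dose is not enough, because that day is still on-treatment under 10.1. The SAP must say how such events with unknown day are classed, for example on-treatment only if the known date parts allow days 1 to 7 after the last dose, and otherwise follow-up. Add a row for year-only starts after the first-dose year.
- **Item missing, or during treatment:** keep the current first-dose imputation.

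Confirm on the CRF that the item is a separate site entry. The cost is a few lines of SAP text and programming, since the protocol says the item is collected. The downside is reliance on the site's timing entry; discrepancies with known date parts should be queried before database lock.
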